markers, such as CRP, in the presence of unrelated inflammatory stimuli, such as concurrent infections and systemic diseases (16,17). For instance, in other diseases like meningitis, blood IL-6 is less specific than IL-6 in the drainage fluid (18). In addition, abdominal drainage fluid is more effective and efficient than routinely collected blood for detecting anastomotic leakage (AL) following colorectal cancer surgery. However, fewer studies have been conducted to predict the recovery of postoperative gastrointestinal function by analyzing drainage fluid. We believe that analyzing postoperative gastrointestinal drainage fluid is of greater clinical importance in predicting postoperative gastrointestinal function.

In our study, we collected abdominal drainage fluid near the anastomosis on the first and third day after laparoscopic colorectal cancer surgery for biochemical and cytological tests. These tests included lactate dehydrogenase (LDH), adenosine deaminase (ADA) and albumin. We also performed conventional cytological tests for neutrophils, lymphocytes, monocytes, etc. In addition, we calculated inflammatory indices such as neutrophil-lymphocyte ratio (NLR), lymphocyte-monocyte ratio (LMR) and prognostic nutrition index (PNI). We also collected peripheral blood for the same cytological indices and evaluated the outcome of the patients' gastrointestinal function recovery using the I-FEED score. In addition, we analyzed the correlation between the above indices and PODG, and combined the inflammation indices of peritoneal drainage and serum to predict the outcome of gastrointestinal function recovery after laparoscopic colorectal cancer surgery, aiming to improve the accuracy and effectiveness of prediction and accelerate patient recovery.

2. Purpose of the study

Primary purpose: The study aims to examine the role of markers lactate dehydrogenase (LDH), neutrophil-lymphocyte ratio (NLR) as markers of inflammation, in the prediction of postoperative gastrointestinal dysfunction (POGD) in drainage fluids on day 1 following laparoscopic colorectal cancer surgery.

Secondary objective: 1. The study aims to examine the role of markers lactate dehydrogenase (LDH), neutrophil-lymphocyte ratio (NLR) as markers of inflammation, in the

prediction of POGD in drainage fluids on day 3 following laparoscopic colorectal cancer surgery.

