2. The study aims to explore the correlation between albumin, adenosine deaminase (ADA), lymphocyte-monocyte ratio (LMR), prognostic nutritional index (PNI) and other inflammation indicators in drainage fluids on day 1 and day 3 following colorectal cancer surgery, and the occurrence of POGD.

3. The study aims to explore the correlation between neutrophil-lymphocyte ratio (NLR), lymphocyte-monocyte ratio (LMR), platelet-lymphocyte ratio (PLR), systemic immune-inflammatory index (SII), and other inflammation indicators in peripheral blood on day 1 and day 3 following colorectal cancer surgery, and the occurrence of POGD.

4. Combined inflammatory markers in peritoneal fluid and peripheral blood to predict POGD.

5. To evaluate the practical application of the I-FEED score in clinical practice.

3. Study endpoints

Primary endpoint:

Grading of postoperative gastrointestinal function (according to the scoring system based on intake, sensation of nausea, vomiting, physical examination, and duration of symptoms (I-FEED). normal (0-2), postoperative gastrointestinal intolerance (POGI) (3-5), and postoperative gastrointestinal dysfunction (POGD) (>6).

Secondary endpoints:

- a. Time to first postoperative deflation.
- b. Time to first postoperative bowel movement.
- c. Time to first postoperative food tolerance.
- d. Morbidity and mortality from 30-day postoperative complications .

4. Outcome Measures

Primary Outcome Measure:

Measurement of drainage fluid lactate dehydrogenase (LDH) and neutrophil to lymphocyte ratio (NLR) on postoperative day 1

Secondary Outcome Measure :

- a. Measurement of drainage fluid LDH and neutrophil to lymphocyte ratio (NLR) on postoperative day 3.
- b. Measurement of drainage fluid albumin, adenosine deaminase (ADA), lymphocyte-monocyte ratio (LMR), prognostic nutritional index (PNI) on postoperative day 1.
- c. Measurement of drainage fluid albumin, adenosine deaminase (ADA), lymphocyte-monocyte ratio (LMR), prognostic nutritional index (PNI) on postoperative day 3
- d. Measurement of blood serum neutrophil-lymphocyte ratio (NLR), lymphocyte-monocyte ratio (LMR), platelet-lymphocyte ratio (PLR), systemic immune-inflammatory index (SII) on postoperative day 1.
- e. Measurement of blood serum neutrophil-lymphocyte ratio (NLR), lymphocyte-monocyte ratio (LMR), platelet-lymphocyte ratio (PLR), systemic immune-inflammatory index (SII) on postoperative day 3.

4.Sample collection

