## 4. Sample size calculation

In a previously published study conducted at our institution, the incidence of postoperative prolonged ileal obstruction (PPOI) was approximately 38.0% (1), a figure we approximated to be equivalent to the incidence of postoperative gastric dysfunction (POGD). The ratio of the POGD group to the non-POGD group was approximately 3:5. Sample sizes were determined based on the primary study endpoints, and the mean lactate dehydrogenase (LDH) in the POGD group on postoperative day 1 (POD.1) was  $(1406.5 \pm 70)$ , as per the pretest results. The mean LDH for the non-POGD group was  $1210 \pm 343$ . Utilizing a one-sided, two-sample unequal-variance t-test with a power of 0.8 and an  $\alpha$ -value of 0.05, calculated using PASS2021 (NCSS, USA), the required number of cases was determined to be 45. The Neutrophil-to-Lymphocyte Ratio (NLR) value for the POD.1 POGD group was  $(156.3 \pm 14.7)$ , while the mean NLR value for the non-POGD group was  $(39.4 \pm 37.5)$ . The calculated sample size for this comparison was 8 cases, with a maximum sample size of 45 cases. In this study, age and TNM stage were primarily controlled as confounders. Assuming that 5 event samples are required to control for each variable, an additional sample of 14 cases is necessary,

bringing the total required sample size to 59 cases. Considering a 5% dropout rate, the final recruitment requirement is 63 cases.

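### Day-1 LDH and NLR are both primary, but the plan gives no success rule or joint error control; if either may carry the claim and neither is truly related to POGD, the false-positive risk is up to 9.75%

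*SAP*

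**What the plan says.** Two markers share primary status. Protocol section 2 opens: "Primary purpose: The study aims to examine the role of markers lactate dehydrogenase (LDH), neutrophil-lymphocyte ratio (NLR) as markers of inflammation", with reference to day-1 drainage fluid. The primary entry in Protocol section 4 (Outcome Measures) is "Measurement of drainage fluid lactate dehydrogenase (LDH) and neutrophil to lymphocyte ratio (NLR) on postoperative day 1".

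SAP section 4 treats them as two separate sample-size problems. For LDH it describes the method as "Utilizing a one-sided, two-sample unequal-variance t-test with a power of 0.8", with an alpha "value of 0.05, calculated using PASS2021 (NCSS, USA), the required number of cases was determined to be 45". For NLR it reports 8 cases without restating alpha, and then takes the larger of the two: "The calculated sample size for this comparison was 8 cases, with a maximum sample size of 45 cases". Confounder control adds 14 cases, "bringing the total required sample size to 59 cases", and a 5% dropout allowance brings recruitment to 63.

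SAP section 5 lists t-tests or Mann-Whitney tests, chi-square tests, Youden cut-offs, logistic regression and ROC analysis. It gives no significance level, no sidedness, no multiplicity method, and no statement of which analysis decides the primary aim.

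**The concern.** When two markers are primary, the plan has to say what counts as success. If either is enough, testing each at 0.05 gives two chances of a false primary finding, and the overall error exceeds the 0.05 in the SAP. If both are needed, it does not. With the rule unwritten, the choice can be made after the results are known, and one significant marker could be reported as meeting the primary aim. Taking the larger of 45 and 8 does not settle the matter, because a study under either rule could be sized that way.

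This matters more for the primary pair than for the other markers, since it is the only part of the plan with a formal alpha and power.

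**Working it through.** **Inputs (SAP section 4).** LDH: 1406.5 (SD 70) with POGD and 1210 (SD 343) without, difference 196.5. NLR: 156.3 (SD 14.7) and 39.4 (SD 37.5), difference 116.9. Group ratio 3:5. Alpha 0.05, power 0.8. N = 45 for LDH, 59 after the confounder addition. The documents give no correlation between the markers, so the values used below are assumptions.

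**Formula.** Welch power from the noncentral t distribution, with v1 = s1²/n1, v2 = s2²/n2, SE = √(v1 + v2), noncentrality = difference/SE, and Satterthwaite degrees of freedom.

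**Step 1: the plan's own figure.**
- One-sided 0.05, as stated: 13 + 22 = 35 patients. SE = √(4900/13 + 117649/22) = 75.66; noncentrality = 196.5/75.66 = 2.60; df = 23.9; power 0.810. So about 35 suffice, and 45 would give 0.889.
- Two-sided 0.05 (equivalently one-sided 0.025): 17 + 28 = 45. SE = √(4900/17 + 117649/28) = 67.01; noncentrality = 2.93; df = 30.6; power 0.810. This reproduces 45.
- NLR with 3 + 5 = 8: power 0.999 at two-sided 0.05 and 0.992 at two-sided 0.025.

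The LDH figure therefore reproduces at two-sided 0.05, not at the level the SAP states.

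**Step 2: error rate if either marker suffices and both nulls are true.** Each test at two-sided 0.05:

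| Assumed correlation of test statistics | Chance of at least one false positive |
|---|---|
| 0 | 1 − 0.95² = 9.75% |
| 0.5 | 9.1% |
| 0.7 | 8.3% |
| 0.9 | 7.0% |

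With one-sided 0.025 per marker, the rate in the expected direction is 1 − 0.975² = 4.94% under independence. If both markers must be significant, the rate cannot exceed 5%.

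**Step 3: LDH power after a correction, at 59 evaluable (22 + 37).** SE = √(4900/22 + 117649/37) = 58.33; noncentrality = 3.37; df = 40.9.
- Two-sided 0.05: 0.908.
- Two-sided 0.025: 0.847.
- The smallest N that holds 0.8 at two-sided 0.025 is 54 (20 + 34), power 0.810.

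Under Holm, LDH is held to 0.025 only if NLR has not been rejected at 0.025. On the SAP's NLR figures that is very unlikely.

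**Step 4: what the margin depends on.** Power at two-sided 0.025:
- 45 patients (17 + 28), Welch: 0.716.
- 59 patients, pooled t-test (simulated): about 0.67.
- 59 patients, Mann-Whitney on normal data (simulated): about 0.71.
- 59 patients, Welch, SD 343 in both groups (assumption): 0.43.

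**The case against.** A reader might infer that the study runs a false-positive risk of nearly 10%. The documents do not support that as a flat statement. It needs an either-marker rule, which is nowhere stated, both nulls true, and independence. Two inflammatory markers from the same fluid may well be positively correlated, which lowers the figure. If NLR differs between groups as the pretest suggests, the only possible false claim in the pair is LDH at 0.05, and Holm would then test LDH at 0.05 too. On the SAP's planning figures, then, the correction changes little; it protects against those figures being wrong. All of this stands, and it is why the rate is given as conditional.

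The sidedness also cuts against a firm figure. If N = 45 reflects a working level of one-sided 0.025 per marker, false claims in the expected direction stay just under 5%. But the SAP does not state that level, so the ambiguity needs resolving.

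A reader might also infer that the correction is safe whatever test is used. It is not. The spare power comes from the 14 cases added for confounders, the Welch test and the pretest SD of 70. SAP section 5 names only a t-test or Mann-Whitney. These weaknesses lie in the plan's own inputs and would reduce uncorrected power as well, but they must accompany any restated power figure.

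Finally, it can be said that a single-centre observational biomarker study needs no formal multiplicity procedure. That may excuse the secondary markers. It does not excuse leaving the primary success rule open.

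**Conclusion.** The point holds in conditional form. Two primary markers, one undivided alpha and no success rule leave the primary error rate undefined. It is up to 9.75% if either marker suffices, both nulls are true and the tests are independent, and about 9.1% to 7.0% at assumed correlations of 0.5 to 0.9. There is no material inflation if both markers are required or if each is tested at one-sided 0.025. Separately, the stated one-sided alpha of 0.05 does not yield N = 45.

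The planned 59 evaluable patients can carry a Holm correction with LDH power of at least 0.85, on the Welch test and the pretest SDs; the 45 cases sized for LDH alone cannot. This is a worthwhile improvement at almost no cost, not a flaw that invalidates the design.

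**What to change.** 1. In SAP section 5, state that either day-1 marker can support the primary aim, name the deciding test (Welch t-test, two-sided), and apply Holm to the LDH and NLR comparisons: smaller p-value against 0.025 and, if that is rejected, the other against 0.05.
2. In SAP section 4, reconcile the sidedness and alpha with N = 45.
3. Restate LDH power at 59 evaluable as 0.85 (tested at 0.025) to 0.91 (tested at 0.05), noting that this assumes Welch, the pretest SDs and use of the 14 confounder cases.
4. Label the day-3, blood and other secondary marker analyses exploratory. Not all are so worded now: the day-3 LDH and NLR objective uses the same language as the primary aim.

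**Cost.** A few SAP sentences and a restated power figure; no more patients, samples or procedures. If NLR is not rejected at 0.025, LDH is judged at 0.025, with power 0.85 instead of 0.91. Holm here covers these two group comparisons only; claims drawn from the ROC or logistic models remain outside it.

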## **5. Statistical analysis**

Statistical analyses were performed by SPSS statistical software v.17.0 (SPSS Inc., Chicago, IL, USA) and R Language v.4.0.3 (R Foundation for Statistical Computing, Vienna, Austria). Measures that met normality were expressed as mean  $\pm$  standard deviation were analyzed using the t-test, and measures that did not meet normality were expressed as median and interquartile range and analyzed using the Mann-Whitney rank sum test. The cutoff value was selected by the use of the Youden index (sensitivity + specificity - 1), and the count data were expressed as number of cases and percentages and analyzed using chi-square test. Predictors of postoperative complications and POGD were studied by univariate and multivariate logistic regression (LR). The diagnostic performance of biomarkers was assessed by receiver operator curve (ROC) analysis.

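### SAP section 4 names two confounders at 5 events each but adds 14 cases, which covers one; two need 27, and the base of 45 does not follow from the stated one-sided test

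*SAP*

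**What the plan says.** SAP section 4 builds the sample size in four steps.

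- **Base.** POGD incidence is taken as 38.0%, and "The ratio of the POGD group to the non-POGD group was approximately 3:5". For day-1 LDH the inputs are 1406.5 ± 70 with POGD and 1210 ± 343 without. The method is given as "Utilizing a one-sided, two-sample unequal-variance t-test with a power of 0.8" and alpha 0.05, and "the required number of cases was determined to be 45". NLR needs only 8, so 45 is carried forward.
- **Confounders.** "In this study, age and TNM stage were primarily controlled as confounders".
- **Addition for confounders.** "Assuming that 5 event samples are required to control for each variable, an additional sample of 14 cases is necessary".
- **Total.** The 14 is added to the 45, "bringing the total required sample size to 59 cases. Considering a 5% dropout rate, the final recruitment requirement is 63 cases".

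No derivation of the 14 is given. SAP section 5 plans univariate and multivariate logistic regression for POGD and sets no limit on the number of predictors. Secondary objective 4 (Protocol section 2) reads: "Combined inflammatory markers in peritoneal fluid and peripheral blood to predict POGD".

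**The concern.** The confounder sentence and the sentence after it do not agree. Two variables at 5 events each call for 10 events, but 14 cases at a 38% event rate bring about 5. Because the 14 is carried into both 59 and 63, a reader cannot tell what adjustment the study was sized for.

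The same paragraph raises a second question. If the 14 is corrected and the 45 left alone, the corrected total still rests on a base that should be checked against its own stated test.

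What is at stake is mainly the multivariable work. SAP section 4 uses a 5-event rule to size the study, but SAP section 5 does not apply that rule to the models. The protocol lists many candidate markers, in two fluids and on two days.

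**Working it through.** **Inputs (all SAP section 4).** Event rate 0.38, or 3/8 = 0.375; 5 events per variable; two variables; base 45; addition 14; dropout 5%; LDH 1406.5 (SD 70) against 1210 (SD 343), difference 196.5; alpha 0.05; power 0.80.

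**1. The stated chain.** 45 + 14 = 59. 59/0.95 = 62.1, so 63. Both totals reproduce, so the 14 feeds directly into the recruitment figure.

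**2. The addition.** Added cases = (variables × 5) / event rate, rounded up.

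| Variables | at 0.38 | at 0.375 | Added cases |
|---|---|---|---|
| 1 | 5/0.38 = 13.2 | 5/0.375 = 13.3 | 14 |
| 2 | 10/0.38 = 26.3 | 10/0.375 = 26.7 | 27 |

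The stated 14 is the one-variable result and brings 14 × 0.38 = 5.3 events.

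**3. The base of 45.** Unequal-variance (Welch) t-test, power from the noncentral t distribution with Satterthwaite degrees of freedom and noncentrality 196.5 / √(70²/n₁ + 343²/n₂), where n₁ is the POGD group.

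| Total (n₁ + n₂) | One-sided power | Two-sided power |
|---|---|---|
| 34 (13 + 21) | 0.794 | 0.682 |
| 35 (13 + 22) | 0.810 | 0.702 |
| 43 (16 + 27) | 0.878 | 0.795 |
| 45 (17 + 28) | 0.889 | 0.810 |
| 59 (22 + 37) | 0.952 | 0.908 |

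For 45 (17 + 28) the standard error is √(70²/17 + 343²/28) = 67.0 and the noncentrality is 196.5/67.0 = 2.93. A simulation of 200,000 runs agrees: 0.809 one-sided at 13 + 22; 0.890 one-sided and 0.812 two-sided at 17 + 28.

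Rounding of the group split moves these totals by about one case: 12 + 22 gives 0.808 one-sided, 16 + 28 gives 0.809 two-sided, and rounding up at exactly 3:5 gives 46 (17 + 29) two-sided. That cannot bridge 35 to 45. The stated one-sided test needs about 35; 45 is consistent with a two-sided test.

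**4. Totals under the additive rule for two variables.**

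- Base 45: 45 + 27 = 72 evaluable; 72/0.95 = 75.8, so 76 recruited.
- Base 35: 35 + 27 = 62 evaluable; 62/0.95 = 65.3, so 66 recruited.

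**5. What 59 patients support when total events are counted.** Expected events are 59 × 0.375 = 22.1 to 59 × 0.38 = 22.4, and 22/5 = 4.4, so at most 4 parameters. Whole-sample sizes for 3, 4 and 5 parameters are 40, 53 and 66 at 0.38, or 40, 54 and 67 at 0.375. The event count will vary (binomial, 59 patients):

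| Events needed | Parameters | P at 0.38 | P at 0.375 |
|---|---|---|---|
| 15 | 3 | 0.985 | 0.982 |
| 20 | 4 | 0.782 | 0.758 |
| 25 | 5 | 0.286 | 0.260 |

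One drainage marker, one blood marker, age and TNM as a single term use all 4. A third marker, or TNM in three levels, makes 5.

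**The case against.** **The two discrepancies nearly cancel.** On the stated one-sided test throughout, the rule gives 62 and 66 against 59 and 63, a shortfall of 3 patients rather than 13. This is correct. The 72 and 76 hold only if 45 is kept, so both pairs should be read together.

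**The primary comparison is not harmed.** This also stands. The t-test sizes do not depend on the 14, and at about 22 events the model can hold LDH, NLR, age and a single TNM term.

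**The 14 may have another origin.** The 45 cases already supply about 17 events, enough for three terms, and one further term adds 14. The SAP does not say this. A consistent total-events count would not give 14 either: four parameters need 53 to 54 cases, only 8 or 9 above 45.

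**The four-term example is assumed.** Neither secondary objective 4 nor SAP section 5 lists the model's terms or says that age and TNM enter the combined-marker model. That is fair: the example shows how quickly the limit is reached and is not the sponsor's specification.

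**The 38% may be too high.** It is a prolonged-ileus figure used as a proxy, and Protocol section 1 puts ileus at about 10–30%. At 30%, 59 patients give 17.7 events, enough for 3 parameters, and the chance of 20 events falls to 0.30. This stands, and it is the reason to base any limit on observed events.

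**A cap on the models goes beyond an arithmetic correction.** It does add something to section 5, but it only carries the SAP's own 5-event rule into the analysis it was used to size.

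**Conclusion.** The concern holds. The 14 covers one of the two named variables; the additive rule as written gives 27, at either 38% or 3:5. The stated one-sided inputs give 35 rather than 45. Two figures behind the 59 and 63 are therefore wrong as written, and the corrected totals are 72 and 76 on the stated base or 62 and 66 on the one-sided base.

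The consequence is moderate. On the SAP's LDH inputs, 59 patients are ample for the day-1 comparison, and on its event rate they support a small adjusted model. The weak point is the combined-marker analysis, where 5 parameters would have their 25 events only 26% to 29% of the time. These results rest on the SAP's means, SDs, event rate and 5-event rule; a lower POGD rate would tighten the limit. The change should be made, but it does not call for more patients.

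**What to change.** 1. **SAP section 4, the 14.** Correct it and state what 59 evaluable patients support, in one of two ways.
   - (a) Say that the 14 covers one covariate and that two would need 27 on the additive rule.
   - (b) Keep 59 and replace the additive step with a total-events statement: about 22 POGD events if the rate is 38%, hence at most 4 parameters at 5 events each, counting every marker, age and every TNM term. Say then that 59 is a chosen size and not an output of the rule, since 4 parameters need 53 to 54 cases.
2. **SAP section 4, the 45.** In the same edit, reconcile it with the stated test: report 35 for the one-sided test or, if the sponsor's calculation was two-sided, say so.
3. **SAP section 5.** Limit the number of parameters in each adjusted POGD logistic model, including the combined-marker model of secondary objective 4, to observed POGD events divided by 5, rounded down.

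The cost is a few sentences, with no change to enrolment or data collection. The drawbacks are a less favourable statement of what 59 patients can support and a cap that may keep some candidate markers out of a combined model.

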## **5. Statistical analysis**

Statistical analyses were performed by SPSS statistical software v.17.0 (SPSS Inc., Chicago, IL, USA) and R Language v.4.0.3 (R Foundation for Statistical Computing, Vienna, Austria). Measures that met normality were expressed as mean  $\pm$  standard deviation were analyzed using the t-test, and measures that did not meet normality were expressed as median and interquartile range and analyzed using the Mann-Whitney rank sum test. The cutoff value was selected by the use of the Youden index (sensitivity + specificity - 1), and the count data were expressed as number of cases and percentages and analyzed using chi-square test. Predictors of postoperative complications and POGD were studied by univariate and multivariate logistic regression (LR). The diagnostic performance of biomarkers was assessed by receiver operator curve (ROC) analysis.

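### Youden cut-offs are chosen and judged in the same roughly 59 patients with no internal validation, so their sensitivity and specificity will be overstated, as may any combined-model AUC

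*SAP*

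**What the plan says.** SAP section 5 covers this in a few sentences. On thresholds: "The cutoff value was selected by the use of the Youden index", defined there as sensitivity + specificity − 1. The same sentence goes on to say that "the count data were expressed as number of cases and percentages and analyzed using chi-square test". On accuracy: "The diagnostic performance of biomarkers was assessed by receiver operator curve (ROC) analysis". Predictors are studied by univariate and multivariate logistic regression.

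Protocol section 2 makes prediction of POGD from day-1 drain LDH and NLR the primary purpose. Its secondary objective 4 is "Combined inflammatory markers in peritoneal fluid and peripheral blood to predict POGD". The SAP does not say how many markers enter that combination, how they are selected, or whether a ROC curve will be drawn for it.

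SAP section 4 arrives at 59 evaluable patients (63 recruited), with an assumed POGD incidence of 38% borrowed from a figure for prolonged ileus. It also says "In this study, age and TNM stage were primarily controlled as confounders" and "Assuming that 5 event samples are required to control for each variable".

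Neither document mentions resampling, cross-validation, a hold-out sample, an external cohort or a cut-off fixed in advance.

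**The concern.** The Youden rule searches all possible thresholds and keeps the one that looks best in the data at hand. Part of that apparent advantage is chance, and it does not carry over to new patients. The same happens when logistic coefficients are fitted and the resulting score is judged on the patients who supplied them. With about 22 events or fewer, the chance component is not negligible.

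Because the study is about prediction, readers will take the sensitivity and specificity at the published threshold as what to expect in their own patients. As the plan stands, those figures will be too favourable on average, and nothing in the plan would show by how much.

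There is a related risk. If a marker is split at its own Youden cut-off and the split is tested by chi-square, the p-value ignores the search and is not valid.

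**Working it through.** **Sample and events.** SAP section 4: 45 + 14 = 59; 59 / 0.95 = 62.1, rounded up to 63. This reproduces the stated totals. Expected events at the SAP's 38%: 59 × 0.38 = 22.4, so 22 POGD and 37 non-POGD. At the 10–30% that Protocol section 1 gives for postoperative ileus: 59 × 0.10 = 5.9 and 59 × 0.30 = 17.7, so about 6 to 18.

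**Marker inputs (SAP section 4, POGD vs non-POGD).** LDH 1406.5 (SD 70) vs 1210 (SD 343); NLR 156.3 (SD 14.7) vs 39.4 (SD 37.5). Assuming normality, the implied AUC is Φ(difference / √(SD₁² + SD₂²)):
- LDH: Φ(196.5 / 350.1) = 0.713
- NLR: Φ(116.9 / 40.3) = 0.998

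The study has many other markers for which the documents give no figures. I therefore added two equal-variance normal markers with *assumed* AUCs of 0.70 and 0.80.

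**Optimism at the Youden cut-off.** In each of 10,000 simulated trials per scenario, the cut-off was chosen in the sample (midway between adjacent values). Its apparent J, sensitivity and specificity were then compared with the true values at that cut-off. Means at 22/37:

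| Marker | J apparent / true | Sensitivity | Specificity | Trials with apparent J above true J |
|---|---|---|---|---|
| LDH (SAP) | 0.59 / 0.52 | 0.98 / 0.93 | 0.61 / 0.59 | 76% |
| NLR (SAP) | 0.99 / 0.97 | 1.00 / 0.99 | 0.99 / 0.98 | 81% |
| Assumed AUC 0.70 | 0.39 / 0.26 | 0.71 / 0.63 | 0.68 / 0.64 | 90% |
| Assumed AUC 0.80 | 0.54 / 0.42 | 0.78 / 0.71 | 0.76 / 0.71 | 88% |

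**Fewer events.**
- LDH: J 0.59 / 0.52 at 18 events and 0.62 / 0.49 at 6 (sensitivity 0.99 / 0.87).
- Assumed AUC 0.70: J 0.40 / 0.26 at 18 events and 0.47 / 0.25 at 6.

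**Single-marker AUC.** For LDH the mean estimate was 0.712 against a true 0.713, with a 95% range of 0.58–0.84. It is imprecise but not biased.

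**Combined model.** Four-term logistic model, 22/37, 1,500 trials, apparent / true AUC:
- LDH + three noise terms: 0.75 / 0.67
- assumed AUC-0.70 marker + three noise terms: 0.74 / 0.66
- LDH + NLR + two noise terms: 0.9996 / 0.995

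With an assumed attainable AUC of 0.70 to 0.80, the optimism was 0.03 to 0.02 with two markers and 0.15 to 0.11 with eight.

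**Chi-square at a Youden cut-off.** For a marker unrelated to POGD (10,000 trials, nominal 5%), the false-positive rate was 22% with the direction fixed in advance and 40% with it free.

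**How much a bootstrap recovers.** J apparent / corrected / true (500 trials × 200 resamples, 22/37):
- LDH: 0.593 / 0.551 / 0.525; share of optimism removed 0.042 / 0.068 = 62%
- NLR: 0.991 / 0.980 / 0.968; 48%
- assumed 0.70: 0.391 / 0.304 / 0.262; 67%
- assumed 0.80: 0.532 / 0.455 / 0.418; 67%

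Sensitivity behaves alike (250 trials × 120 resamples): LDH 0.971 / 0.946 / 0.929. For the four-term AUC the correction was close to complete (200 trials × 100 resamples): LDH + three noise terms 0.739 / 0.672 / 0.672; assumed 0.70 + three noise terms 0.737 / 0.668 / 0.663.

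**The case against.** The direction of the bias is not in dispute; its weight is.

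- **Size on the SAP's own figures.** J is overstated by only about 0.07 for LDH and 0.02 for NLR. The larger gaps rest on assumed AUCs. This stands, and the assumed-AUC results should be read as a range. They remain relevant because the pretest values may not hold and many further drain and blood markers could be given Youden cut-offs.
- **What is untouched.** The group comparisons by t-test or Mann-Whitney and the single-marker AUCs are unaffected. This stands and limits the severity.
- **Combined model.** The SAP does not commit to a combined ROC, and a model holding both LDH and NLR at their pretest values shows almost no optimism. This stands: the problem matters only if NLR is weaker than in the pretest or is left out.
- **Chi-square.** Count data may simply mean variables such as sex or stage. This is fair, so the point is a conditional caution.
- **Low event counts.** The 10–30% is a literature range for ileus under varying definitions, while 38% is the institution's own figure. Six events is the extreme bound. But the 38% is itself a proxy for POGD, so a lower count cannot be dismissed.
- **Partial remedy.** The bootstrap leaves a third to a half of the cut-off optimism in place. This stands and is why the cut-offs also need an exploratory label.

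**Conclusion.** The concern holds. Following SAP section 5 as written gives sensitivity and specificity at the Youden cut-off that are too high on average. At 22 events, J is overstated by about 0.07 for LDH and 0.02 for NLR on the SAP's figures, and by about 0.11 to 0.13 for markers of assumed AUC 0.80 and 0.70. The overstatement grows as events fall. A combined-model AUC, if reported, could be inflated by anything from almost nothing to about 0.15, depending on the number and strength of the markers.

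These sizes assume normally distributed markers. The direction of the bias follows from choosing and judging the cut-off in the same patients. The primary single-marker AUCs are not biased, so this is a change that should be made, not a flaw that invalidates the study.

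**What to change.** Amend SAP section 5 as follows.

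1. Report the AUCs of day-1 drain LDH and NLR with 95% confidence intervals as the main accuracy results.
2. Add bootstrap internal validation (for example 1,000 resamples) that repeats the cut-off choice, any variable selection and the model fitting in every resample. Give optimism-corrected sensitivity, specificity and any combined-model AUC beside the apparent values. Label the Youden cut-offs exploratory, and say that the corrected sensitivity and specificity probably remain somewhat high.
3. Keep markers continuous in the logistic models, and report no unadjusted chi-square p-value for a marker split at its own Youden cut-off.
4. State whether a combined-model ROC will be reported and how its markers are chosen. Set the number of terms from the observed events at the SAP's own 5 per variable, counting age and TNM stage: 22/5 = 4.4, so 4 terms; 18/5 = 3.6, so 3; 12/5 = 2.4, so 2; 6/5 = 1.2, so 1. If age and TNM stage take one term each, that leaves two marker terms at 20–24 events, one at 15–19 and none below 15. Otherwise use penalised regression.

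The cost is SAP wording and a few lines of R, which the SAP already names. No new data or patients are needed. The downside is lower reported accuracy and fewer markers in the combined model, possibly none without penalisation if events fall below 15.
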